The statistical analysis strategy will be split into three stages: (1) analysis of first follow-up findings in relation to baseline findings; (2) analysis of second and subsequent follow-up findings in relation to baseline and first follow-up findings, and (3) analysis of rates of symptomatic CRC in the years after final endoscopic examination.

Analyses will be performed both including and excluding those with first follow-up less than 3 years after baseline, as this may be a reflection of clinical opinion of extra high risk. Results of all analyses will be confirmed by internal cross-validation.

For questions 6 – 8 our statistical analyses will focus on the long-term CRC incidence after

baseline. To assess the effect of surveillance on CRC risk, we will compare the incidence of CRC both in the absence and presence of surveillance, and compare CRC risk with that expected in the general population. Cox proportional hazard models will be used to assess the relationship between baseline characteristics and CRC risk to identify subgroups in which CRC risk is low enough to justify less intensive surveillance and reclassification of risk. In those who benefit from surveillance, the CRC risk will be examined after multiple exams to estimate when surveillance could safely stop, or multiple intervals to estimate the appropriate interval length between surveillance exams.

Additional health economic analyses will be conducted to estimate the cost implications of alternative surveillance strategies (question 9).

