# 2.7 Outcome measures

- Colorectal cancer diagnosed symptomatically or at follow-up colonoscopy.
- Multiple or advanced adenomas detected at follow-up colonoscopy. Advanced adenomas are defined as adenomas larger than 1 cm, with severe dysplasia or with tubulovillous or villous histology.
- The subsite of adenomas which will inform about whether or not flexible sigmoidoscopy is adequate for surveillance.
- For the psychological impact analysis: anxiety, bowel cancer worry, number of GP visits and bowel symptoms.
- For the economic analyses: cost per cancer avoided and cost per life year saved

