### 2.9.3 Analysis of colorectal cancer occurrence after endoscopic examination

The analyses above will be complemented by analyses of subsequent clinical CRCs in the follow-up period where available. Such events are rare and estimates will therefore be imprecise, but the analysis will add some value to the exercise, by enabling us to assess the trade-off between harvest of polyps at subsequent examination and expected number of cancers occurring before the subsequent examination. Again the analysis will proceed in steps of increasing complexity, beginning with simple description of rates of cancers by time since and findings at last examination, through regression modelling to formal multistate models.

We will assess the absolute risk of CRC using Kaplan-Meier curves and will compare the incidence of CRC to that expected in the general population, both in the absence and in the presence of surveillance. We will use Cox proportional hazards models to assess the effect of surveillance on the risk of CRC, with the number of follow-up visits included as a time-varying covariate.

The models will also be used to assess the relationship between patient, polyp and procedural characteristics at baseline and CRC risk. We will use univariable models to estimate unadjusted hazard ratios and will use multivariable models to estimate the effect of surveillance adjusted for patient, polyp and procedural characteristics and to identify independent predictors of future CRC risk. The risk factors identified in the multivariable models will then be used to aid in the creation of distinct subgroups. These subgroups will then be scrutinised to determine whether in any subgroup the CRC risk after baseline is low enough relative to the general population to not warrant surveillance. Conversely, in subgroups that do appear to benefit from surveillance, the results will be examined to see whether the risk of CRC becomes low enough after a certain number of exams in order for surveillance to safely cease.

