In order to examine appropriate surveillance interval lengths, we will analyse the yield of advanced adenomas and CRC at surveillance visits by interval in patients who attended follow-up after baseline. In the high-risk group we will also examine the effect of a short vs a longer surveillance interval (one year as recommended vs longer than one year) on long-term CRC incidence. In order to investigate this, we will create crude groupings based on the interval to first follow-up exam and the incidence of CRC between groups will be compared.

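### The high-risk comparison of a one-year with a longer first interval groups patients by a later event, with no time zero or rule for cancers before that exam, and is expected to flatter the longer interval

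*Combined protocol and SAP*

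**What the plan says.** The last paragraph of section 2.9.3 takes up interval length. In the high-risk group the contrast is "one year as recommended vs longer than one year", the outcome is long-term CRC incidence, and the method is one sentence: "we will create crude groupings based on the interval to first follow-up exam and the incidence of CRC between groups will be compared".

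Four other statements bear on it.

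- **Time origin.** Section 2.3.1 says "For questions 6 – 8 our statistical analyses will focus on the long-term CRC incidence after" baseline (the sentence runs over a page break). Section 2.9.3 does not restate an origin for the interval groups.
- **Outcome.** Section 2.7 lists "Colorectal cancer diagnosed symptomatically or at follow-up colonoscopy", so symptomatic diagnosis stands apart from detection at a follow-up exam, and both count.
- **Models.** Section 2.9.3 also plans Cox models "with the number of follow-up visits included as a time-varying covariate", and multivariable models "to estimate the effect of surveillance adjusted for patient, polyp and procedural characteristics". Both are described for the effect of surveillance; neither is tied to the interval groups.
- **Selection.** Section 2.3.1 concedes that a first follow-up before 3 years may be selective, "as this may be a reflection of clinical opinion of extra high risk".

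For the interval groups the plan names no landmark, delayed entry or weighting. It does not say where patients go who develop CRC, die or are censored before a first follow-up exam.

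**The concern.** Exposure is defined by something that happens after follow-up has begun. To be placed in the longer group, a patient must reach a late exam without a symptomatic CRC diagnosis. A patient whose cancer surfaces first has no interval and belongs to neither group. Time before the exam is therefore free of symptomatic CRC by construction, and the longer group has more of it.

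Starting the clock at the exam removes that guaranteed event-free time. It also discards the cancers that appear while a patient waits, which are the ones a longer interval might allow.

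Confounding by indication is expected to push the same way. If patients judged to be at higher risk are examined sooner, the one-year group will look worse for reasons unrelated to the interval.

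Research question 8 asks for intervals that do not lead to too many interval cancers, and section 2.2.4 hypothesises that less surveillance than is now recommended is enough. An error that favours longer intervals favours that hypothesis. This is also the plan's only explicit contrast of one year with longer on long-term CRC incidence.

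**Working it through.** **The plan's own figure.** There is none to reproduce: the documents give no sample size, power or expected effect for this comparison.

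**Step 1: the mechanism in closed form.** Take a constant CRC hazard, no true effect, a clock from baseline, and CRC found at the exam itself left out. Each group is event-free until its exam, so with T years of follow-up and exams at 1 and L years the longer/short rate ratio is about

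(T − L)/(T − 1).

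- T = 6, L = 3: 3/5 = 0.60.
- T = 10, L = 3: 7/9 = 0.78.

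This isolates the mechanism but overstates its effect, because section 2.7 counts CRC found at follow-up colonoscopy.

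**Step 2: simulation with exam-detected CRC counted.**

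Inputs from the documents:
- 4.5 per 1,000 per year, the high-risk rate in section 2.8, used here as the rate of preclinical onset;
- follow-up of 6 years (section 2.8, updated calculation) and about 10 years (section 2.3.3, additional health economic analysis).

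Assumptions not in the documents:
- mean preclinical duration 2 or 4 years;
- short exams at 0.75–1.25 years, longer exams at 2–4 or 1.25–5 years;
- 30% never examined;
- other-cause death 2% per year;
- an exam finds any preclinical cancer present but prevents none.

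The reference ratio follows everyone who would attend from baseline, by intended interval, whether or not they reach the exam. It exceeds 1 although no harm was built in: a later exam finds more accumulated preclinical disease, and less time remains for the short group to catch up. The grouped ratio uses only patients whose first exam took place, with the clock from baseline.

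| Follow-up (years) | Preclinical duration (years) | Longer exam (years) | Reference ratio | Grouped ratio | Grouped/reference |
|---|---|---|---|---|---|
| 6 | 2 | 2–4 | 1.09 | 0.78 | 0.71 |
| 6 | 2 | 1.25–5 | 1.09 | 0.75 | 0.69 |
| 6 | 4 | 2–4 | 1.24 | 1.00 | 0.80 |
| 6 | 4 | 1.25–5 | 1.26 | 0.98 | 0.78 |
| 10 | 2 | 2–4 | 1.01 | 0.84 | 0.84 |
| 10 | 2 | 1.25–5 | 1.01 | 0.83 | 0.82 |
| 10 | 4 | 2–4 | 1.06 | 0.93 | 0.88 |
| 10 | 4 | 1.25–5 | 1.06 | 0.91 | 0.87 |

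The last column was computed before rounding. The table is one run of 6 million patients per row. Repeat runs move ratios by a few hundredths, and the ranges quoted elsewhere in this point allow for that. The longer interval looks 12% (1 − 0.88) to 31% (1 − 0.69) better than it is. In the same run, 15% to 36% of CRCs under the longer strategy surface before the exam and drop out of its group.

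**Step 3: other rules, same assumptions.**

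| Rule | Longer/short ratio |
|---|---|
| Clock starts at the exam, later CRC only | 0.70–0.93 |
| Symptomatic diagnostic colonoscopy counts as the first exam | 1.52–1.75 |
| Never-examined patients join the longer group | 1.04–1.16 |
| Landmark at 1.25 years | 1.12–1.84 |

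**Step 4: precision.** The updated calculation in section 2.8 gives about 50 CRCs in the high-risk group at 6 years, reading its three counts as low, intermediate and high risk. With equal groups, power to detect a ratio of 0.60 at two-sided 5% is Φ(√(50 × 0.25) × |ln 0.60| − 1.96) = Φ(1.81 − 1.96) = Φ(−0.15), or 44%.

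**The case against.** The strongest reply is that one sentence is being read too literally, and part of that stands.

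- **Direction.** Section 2.9.3 does not define the first follow-up exam. If a colonoscopy prompted by symptoms counts, the ratio turns against the longer interval. If never-examined patients join the longer group, it lies near the reference. Section 2.7 separates symptomatic diagnosis from detection at follow-up, which favours the reading used here. Still, a reader who infers that the direction is certain goes beyond the text.
- **Adjustment.** A reader might take the word crude to mean unadjusted. It describes the groupings. No model is named for the comparison, so lack of adjustment is an inference, and the same section has multivariable models that could be applied.
- **Other evidence.** A reader might infer that all the plan's evidence on intervals rests here. It does not. Section 2.3.1 also looks at CRC risk after multiple intervals, section 2.9.1 offers a multistate model as a formal criterion for intervals, and section 2.9.3 weighs polyp yield against cancers expected before the next exam.
- **The 3-year rule.** Section 2.3.1 says "Analyses will be performed both including and excluding those with first follow-up less than 3 years after baseline". A reader might infer that this deletes the one-year group. The sentence precedes the separate paragraph on questions 6–8, and one of its two versions keeps those patients, so it is no ground for criticism here.
- **Importance.** This is one comparison with about 50 CRCs at 6 years, and section 2.9.3 already warns of imprecision. That limits the weight of the point, but a wide confidence interval does not correct a shifted estimate.

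None of this supplies a time zero or a rule for cancers before the exam.

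**Conclusion.** The point holds as an expected bias on the ordinary reading, and should be fixed. That reading has a clock from baseline, and patients with symptomatic CRC before any exam left without an interval.

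Under the assumptions above, the grouped ratio is about 0.75–1.00 against a reference of 1.07–1.27 at 6 years, and 0.83–0.93 against 1.01–1.06 at 10 years. These figures illustrate the effect and are not estimates for this cohort. They depend mainly on exam timing and preclinical duration, which the documents do not give. The 0.60 and 0.78 in step 1 should not be quoted as the size of the bias, because they leave out exam-detected CRC.

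Confounding by indication is not in these figures and would probably add to them. Across classification rules that the text leaves open, the ratio runs from about 0.7 to 1.75. That spread is reason enough to settle the rule before analysis.

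**What to change.** Replace the crude grouping with a comparison of the two interval strategies from baseline, in all high-risk patients, by clone-censor-weight. The SAP should state that:

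1. Time zero is the baseline colonoscopy. The one-year window, and what counts as a follow-up exam (including how a colonoscopy prompted by symptoms is treated), are fixed in advance.
2. Each patient enters under both strategies and is censored from one when the record no longer fits it. Patients with CRC before any exam, and never-examined patients, stay under every strategy they still fit.
3. Symptomatic and exam-detected CRC both count, and the handling of death and loss to follow-up is given.
4. Weights and adjustment use the patient, polyp and procedural characteristics already named in section 2.9.3.

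A landmark at the end of the one-year window should serve only as a sensitivity analysis. It drops CRC found at the one-year exam but keeps the equivalent undetected cancers in the comparison group, so it overstates the ratio (1.12–1.84 above).

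The cost is SAP wording, modest programming on data already held, and somewhat wider confidence intervals from the weights with about 50 CRCs at 6 years. Weighting handles recorded characteristics only; clinical judgement that was not recorded remains a limitation to report.

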# 2.10 Research Governance

An ndependent Trial Steering Committee has been established, which, in addition to reporting to the funders on the progress of the study, will also consider ethics and governance issues as they arise. The study will be undertaken in full compliance with the Research Governance Framework. We anticipate that the major governance issue relates to data protection and we intend to seek exemption under Section 60 from the Health and Social Care Act through PIAG.

### Appendix 1.0, supplementary information

# Clarification of the study datasets and statistical analysis plan for the 'All Adenomas study'.

# Background

In 2006 we initiated the 'Intermediate Adenoma study' (full study title "Frequency of follow-up for patients with intermediate grade adenomas"). The aims, objectives and planned analyses of this study were outlined in the original protocol; the main focus being the investigation of surveillance colonoscopy among individuals classed as 'intermediate-risk' after polypectomy. In order to identify intermediate-risk patients, we collected information from many individuals from both screening and hospital settings. This study was funded by the National Institute for Health Research – Health Technology Assessment programme (NIHR-HTA), reference NIHR-HTA 04/33/01, and supported by a Cancer Research UK (CR-UK) programme grant, reference C8171/A16894.

In 2017, the Cancer Screening and Prevention Research Group were awarded an additional grant (reference NIHR-HTA 15/80/13) to expand the remit of this study to investigate all risk-groups (low-, intermediate- and high-risk), using the individuals already identified as having adenomas as part of the original Intermediate Adenoma study. The study protocol was amended to "Frequency of follow-up for patients with low-, intermediate- and high- risk colorectal adenomas", or short title the 'All Adenomas study'. It is additionally supported by a new CR-UK programme grant, reference C8171/A25004. The amendment to the All Adenomas study was approved by the London - Hampstead Research Ethics Committee (REC) and Health Research Authority in May 2017 (IRAS reference 55943, REC reference 06/Q0501/45).

The changes made to the protocol V2.0, 14/03/2017, were intentionally minimal – to reflect the original purpose of the Intermediate Adenoma study as published in 2017. However, additional clarification has been requested – which this supplementary document aims to provide, in three areas:

- a) The composition of the study dataset(s).
- b) Statistical analyses already completed for the Intermediate Adenoma study, vs. planned All Adenomas study analyses
- c) Collaboration with Health Economic Research Centre (HERC), University of Oxford, to perform a health economic analysis.

#### Clarifications

#### a) Study Datasets (see Protocol sections 2.3 and 2.8).

The Intermediate Adenoma study was designed to create one study database from a combination of the screening and hospital datasets. However, the hospital dataset alone provided sufficient power to conduct the analyses, allowing us to reserve the screening dataset for validation of the analyses in the hospital dataset.

	Patients with intermediate adenomas (n)		
Sample size required for analysis:	Baseline	≥ 1 follow-up colonoscopy	≥ 2 follow-up colonoscopies
Endpoint	Colorectal cancer	Advanced adenoma	Advanced adenoma
Total number of endpoints required	60	198	36
Total number of patients required	10,000	6,600	1,200
Actual number of patients obtained from UK hospital databases (endoscopy / pathology data). Data to end 2014 (the Intermediate Adenoma study cohort)	11,944	7,046	3,773

#### Protocol sample size table, section 2.8.2 - updated

The hospital dataset is comprised of endoscopy / pathology data originating in the participating hospitals, colorectal cancer incidence data from NHS Digital, ONS mortality data (via NHS Digital), National Records of Scotland mortality data and cancer registration data from NHS National Services Scotland. This is the dataset that we will be using to conduct the All Adenomas study; the 'All Adenomas study database'.

Of the six additional screening datasets listed in section 2.8.1 of the protocol, several datasets were excluded for reasons such as data security, permission denied, insufficient data and data not being electronically linked (so that manual data collection would be too costly and lengthy to obtain). Three datasets remained: The UK Flexible Sigmoidoscopy Screening Trial, the English data from the UK National Pilot of FOBT screening and the Kaiser Permanente dataset. These three datasets have been combined to make an independent 'screening dataset' which is not linked to the All Adenomas study database. The screening dataset will be used to validate the findings in the All Adenomas study database.

#### b) All Adenomas statistical analysis plan

The Intermediate Adenoma study statistical analyses have been completed and already reported. Further analysis of the intermediate-risk patients will occur within the All Adenomas study as some outcomes warrant re-examination with extended follow-up time, which will also allow investigation by the subsites of proximal versus distal colorectal cancer (CRC) due to an increased number of cancers diagnosed during this time. Four new research questions were added to the protocol as part of the All Adenomas study amendment (approved May 2017); questions 6-9 of section 2.3.1 and repeated below. The statistical analysis plan is given in protocol section 2.9. and applies to examining overall CRC, CRC by subsite and mortality.

Qu. 6. What is the risk of CRC in each adenoma risk-group defined according to current UK adenoma surveillance guidelines:

a) What is the long-term CRC risk in those who have no surveillance?

b) What is the long-term CRC risk in those who do have at least one, or two or more surveillance exam(s)?

c) Are there sub-groups in which CRC risk is low enough not to warrant surveillance?

d) Among those whose risk is determined high enough to require surveillance, when would CRC risk become sufficiently low to safely stop surveillance?

Qu. 7. Should risk-groups be redefined based on long-term CRC risk such that some patients might be reclassified as lower risk?

Qu. 8. What are appropriate surveillance intervals within defined risk groups to warrant colonoscopy but not result in unacceptably high interval cancers?

Qu. 9. What are the health and economic impacts of refined risk groups and surveillance intervals?

The psychological impact analysis has been completed for the Intermediate Adenoma study (protocol section 2.1.2. and 2.3.2), and will not be repeated for the All Adenomas study.

The health economic impact analysis will be updated for the All Adenomas study, see information below.

#### c) Collaboration with HERC, University of Oxford, to perform a health economic analysis (Protocol section 2.3.1, research question 9; and Protocol section 2.3.3)

The Intermediate Adenoma study reported on the health economic (HE) evaluation of different surveillance strategies for the intermediate-risk group, as described in protocol section 2.1.3 (first 3 bullet points) and section 2.3.3.

A new health economic analysis will be performed by [name] and team at HERC, University of Oxford, for all risk groups, for the All Adenomas study. This correlates to research question 9, protocol section 2.1.3 (in the final bullet point) and 2.3.1. The All Adenomas study HE objectives are described further in the protocol section 2.3.3. and page 9 'Additional Health Economic Analysis'.

For the purpose of the additional HE analyses, we will request cancer staging data from NHS National Services Scotland and Public Health England – Office for Data Release. When available, this extra data will be incorporated into the All Adenomas study database and a minimal sub-set of data on the

Page 21 of 23 Version 4.0 14/03/2019 study participants with adenomas at baseline only will be shared with HERC to conduct the HE analysis. A data flow diagram is provided on the next page.

[figure not shown]
### PHE-ODR data items requested.

We have minimised the amount of data requested to enable reconciliation of the cancers reported in the NCRAS cancer registration tables with the existing All Adenomas study database. Patient ID, tumour ID, and event ID will be requested to help incorporate each record to our study database. ONSID is requested to facilitate matching to cancer data provided by ONS/ NHS Digital to prevent erroneous double counting of cancers, which may bias the study results.

As multiple events may happen in the same month, we need to request the following exact dates to conduct the health economic analysis, rather than month and year only: diagnosis date, date of first recorded event in treatment table, date of first recorded surgery in treatment table, Trust code of first recorded surgery in treatment table.

